# 3.3 Registration and Randomization

All participants must sign the consent form prior to determination of eligibility for this study. All participants who meet the inclusion/exclusion criteria may be registered. Registration will occur following verification of eligibility by the treating physician.

Participants should receive their first study treatment within 2 weeks of registration.

No randomization is required; all participants will receive the same vaccine regimen.

# 4.0 STUDY DRUG (6MHP and MONTANIDE ISA-51)

# 4.1 Peptide Synthesis

The vaccine drug product (6MHP) to be administered consists of 6 peptides. All peptides were synthesized directly from amino acids by Multiple Peptide Systems (now Polypeptide Group, San Diego, CA) under GMP conditions. Recombinant vectors in bacteria or viruses were not used. The synthetic peptides were purified by HPLC. The identity of the synthetic peptides has been confirmed by verifying their mass and amino acid sequences by mass spectrometry. Details of the synthesis, certificates of analysis, and technical summaries are included in the IND application.

# 4.2 Storage of Individual Peptides

Each bulk peptide was supplied to the HITC as lyophilized powder without excipients and stored at a temperature  $\leq$  -70°C and protected from light.

### 4.3 Reconstitution and Vialing of the Vaccine

Lyophilized peptides were reconstituted, mixed and vialed under GMP conditions by Clinalfa (Merck Biosciences AG, Laufelfingen, Switzerland). Lyophilized peptides were supplied to the HITC as individual use vials. Lot release testing of the final vialed peptide has also been completed by Clinalfa in accord with FDA guidelines. Details of the vialing are included in the IND application.

#### 4.4 Vaccine Storage

The vials of lyophilized peptide are stored by the HITC at a temperature  $\leq$  -70°C and protected from light. Once thawed, the vial(s) must be used for preparation of the vaccine within 24 hours.

#### 4.5 Lot Testing

Each lot of peptide vaccine is evaluated as required by the FDA for identity, sterility, general safety, purity, and pyrogenicity. The details of these tests are outlined in the IND application.

#### 4.6 Stability testing

The peptide vaccine will undergo stability testing as described in Appendix 7.

# 4.7 Labeling

Each vial of lyophilized peptide is labeled with the following information:

- Short name of the product
- Product number
- Proper name of the product
- Name and address of the vialing facility
- Lot number
- Date of manufacture (the date of vialing the reconstituted peptides)

- Serial number
- Quantity of each peptide per vial
- Vial contains no preservative, store at ≤ -70°C
- "Caution: New Drug Limited by US Federal law to investigational use"

### 4.8 Montanide ISA-51

Montanide ISA-51 is available from Seppic, Inc. (Fairfield, NJ). A drug master file for Montanide ISA-51 is filed with the FDA and is cross-referenced in the IND application.

Class II MHC-restricted melanoma peptides (6-MHP; 200 mcg) in aqueous solution are mixed 1/1 with Montanide ISA-51 to form water-in-oil emulsions.

### 4.9 Study Drug Accountability

The investigational drug will be stored in accord with directions specified in Section 4 of the protocol in a secure area with the UVA-HITC laboratories. Study drug accountability is maintained using the InvestMed database.

### **5.0 IPILIMUMAB**

### 5.1 Packaging and Labeling

Ipilimumab (YERVOY®) is an FDA approved drug for usefor the treatment of patients with unresectable or metastatic melanoma. The study drug is manufactured by Bristol Myers-Squibb and is packaged and labeled in accord with the package insert. It is provided as a sterile aqueous liquid at 5 mg/ml in single-use vials with either of two volumes (10 ml or 40 ml).

#### 5.2 Storage

Ipilimumab is stored refrigerated at  $2^{\circ}C - 8^{\circ}C$  ( $36^{\circ}F-46^{\circ}F$ ). Vials are to be protected from light and should not be frozen

# 6.0 TREATMENT PLAN

#### 6.1 Management of Participants

This study will be conducted on an outpatient basis, with participants scheduled to be evaluated as needed for clinical care, and as specified in the study calendar (Appendix 1), through 24 months (or more often if needed for testing or medical reasons). Participants will be off treatment follow-up at the end of 24 months, or when another therapy is initiated, whichever occurs first. Once off treatment follow-up, participants will be followed yearly for progression-free survival and overall survival.

# 6.2 Administration of 6MHP

6.2.1 Overview

The vaccine regimen will be the same for all subjects. Days 1, 8, 15, 43, 64, 85: 200 mcg each of the 6 peptides (Table 1), emulsified in Montanide ISA-51 adjuvant (2 ml total will be administered). Each of vaccines 1-3 will be administered subcutaneously (50%) and intradermally (50%) at one skin site. If the site of vaccines 1 or 2 has severe inflammation or ulceration, the next vaccine may be placed near the original site. Vaccines 4-6 will be administered at a different site than vaccines 1-3, but vaccines 4-6 will all be

administered at one site. If the site of vaccines 4 or 5 has severe inflammation or ulceration after 1-2 vaccines, the next vaccine may be placed near the site designated for vaccines 4-6.

On days when both ipilimumab and vaccine are administered, the vaccine may be administered before or after ipilimumab, but preferably before.

6.2.2 Dose Calculations

At each designated time-point, 200 mcg each of the 6 peptides (Table 1), emulsified in Montanide ISA-51 adjuvant (2 ml total) will be administered.

6.2.3 Pre-Medications

None required.

6.2.4 Preparation of Study Drug

Directions on how to prepare the investigational drug will be provided. The prepared peptide vaccines, containing 2 ml of peptide emulsion, will be stored in a plastic syringe and delivered to the clinicians in a plastic bag. This bag with the syringe will be stored at room temperature until the vaccine is administered. Ideally, the vaccine should be administered within 1-2 hours after mixing. If the vaccine is not administered within 4 hours after mixing, it should be discarded.

#### 6.2.5 Post-Vaccination Observation

All participants will be closely observed for adverse events for at least 20 minutes following each vaccination. Any time thereafter, participants should report any adverse events to the research coordinator or research clinician.

### 6.3 Administration of Ipilimumab

#### 6.3.1 Overview

Ipilimumab will be administered in accord with the official prescribing information: 3 mg/kg intravenously once every 3 weeks, for 4 doses.

6.3.2 Pre-Medications

None required.

#### 6.4 Dose Modifications

6.4.1 6MHP

There will be no dose modifications of the vaccine components

6.4.2 Ipilimumab

In the event of treatment related toxicity, the dose of ipilimumab should be modified in accord with current practice guidelines. Recommendations are also provided in the package insert. Immune-related adverse events should be managed per standard clinical practice and in accord with the package insert for YERVOY® (ipilimumab) and the Immune-mediated Adverse Reaction Management Guide, available from Bristol-Myers Squibb. (https://www.hcp.yervoy.com/pages/rems.aspx)

### 6.5 Dose Delays

Protocol treatment includes both the 6MHP vaccine and ipilimumab. Either or both may be delayed for any of the following reasons:

6.5.1 Dose Delays Due to Toxicity

- In circumstances where assessment of an AE is limited, such as by intercurrent illness, or when laboratory studies are required to assess for other causes of toxicity, the vaccine schedule may be interrupted for up to 21 days. Delay of one vaccine administration by up to 21 days will not be considered a protocol violation if due to an AE, regardless of attribution. If more than one vaccine is delayed by 21 days due to an AE, regardless of attribution, vaccine treatment should be discontinued, though the other systemic therapy may be continued.
- Dose delays for ipilimumab will follow standard clinical guidelines.

### 6.5.2 Delayed Visits for Reasons Other Than Toxicity

A schedule for return visits should be established at the first visit. If a participant misses a treatment, the missed treatment will be administered as soon as possible, so that subsequent treatments will be given in the appropriate intervals. Treatment may be continued for an additional time period, if needed. Participants who are treated outside of the established schedule should return to the original schedule as soon as possible

The table below (Table 7) defines what constitutes a delayed visit, whether the participant should continue to be treated, and whether a protocol violation should be reported and recorded. The range of days is counted from the original scheduled date.

Table 7. Delayed Visit for Reasons other than Toxicity				
Treatment Period	Range of Days	Participant Treatment	Protocol Deviation	
Vaccine 1*/Ipilimumab 1				
Day 1	± 2 days	Vaccine, Labs, Ipilimumab	No	
	$\pm$ 3 to 7 days	Vaccine, Labs, Ipilimumab	Yes	
	$\pm$ 8 or more days	Labs	Yes	
Vaccines 2-3*				
Days 8, 15	± 2 days	Vaccine/Labs	No	
	$\pm$ 3 to 7 days	Vaccine/Labs	Yes	
	$\pm$ 8 or more days	Labs	Yes	
Biopsy/Ipilimumab 2				
Day 22	± 2 days	Labs, Biopsies, Ipilimumab	No	
	$\pm$ 3 to 7 days	Labs, Biopsies, Ipilimumab	Yes	
	$\pm$ 8 or more days	Labs	Yes	
Vaccine 4*/Ipilimumab 3				

Davs 43	± 2 days Vaccine, Labs, Ipilimuma		No
	$\pm$ 3 to 7 days	Vaccine, Labs, Ipilimumab	Yes
	± 8 or more davs	Labs	Yes
Assessment			
Day 57	±7 days	Scans**	No
	$\pm$ 8 to 14 days	Scans	Yes
	$\pm$ 15 or more days	Scans	Yes
Vaccine 5*/Ipilimumab 4			
Day 64	± 7 days	Vaccine, Labs, Ipilimumab	No
	$\pm$ 8 to 14 days	Vaccine, Labs, Ipilimumab	Yes
	$\pm$ 15 or more days	Labs	Yes
Vaccine 6*			
Day 85	± 7 days	Vaccine, Labs, Scans**	No
	$\pm$ 8 to 14 days	Vaccine, Labs, Scans**	Yes
	$\pm$ 15 or more days	Labs/Scans	Yes
Assessment			
Day 92	± 7 days	Labs	No
	$\pm$ 8 to 14 days	Labs	Yes
	$\pm$ 15 or more days	Labs	Yes
Follow-up			
FUv1 and FUv2	± 14 days	Labs/Scans**	No
	$\pm$ 15 or more days	Labs/Scans	Yes
– "			ļ
Follow-up			
FUv3, FUv4, FUV5	$\pm$ 28 days	Labs/Scans**	No
	$\pm$ 29 or more days	Labs/Scans	Yes

\* A participant will be taken off protocol treatment if more than one vaccination is delayed [± 3 to 7 days] during the treatment period.

\*\* CT scans on days 57, 85, FUv1, FUv2, FUv3, FUv4, FUv5 should also be completed within the specified time limits. The scan at day 57 is to measure response, with confirmatory scans at day 85 only if needed. Followup scans beyond day 85 may be performed earlier or more frequently than specified in the protocol if indicated as part of clinical care. If earlier or more frequent scans have been performed for clinical care, it is not a violation to omit scans on followup dates if they have been performed within 3 months prior.

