# Treatment Regimen:

All patients will receive 1) the 6MHP vaccine administered in Montanide ISA-51 adjuvant (incomplete Freud's adjuvant) and 2) ipilimumab, an anti-CTLA-4 blocking antibody. Ipilimumab will be administered at 3 mg/kg IV infusion on days 1, 22, 43, and 64. Vaccines will be administered days 1, 8, 15, 43, 64 and 85. On days when both ipilimumab and vaccine are administered, the vaccine may be administered before or after ipilimumab, but preferably before. All peptide vaccines will be administered intradermally and subcutaneously. Blood and biopsy samples of a vaccine-draining node and tumor will be analyzed for immunologic changes. Details are provided in the protocol schema (Figure 1, Figure 2, Figure 3) and in the study calendar (x-page; Appendix 1).

Figure 2: Protocol Schema Cohort 2

Figure 3: Protocol Schema Cohort 3

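### Table 7, read as printed, lets ipilimumab dose 4 be given 12 days after dose 3 without a deviation, although section 6.3.1 specifies every 3 weeks

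*Combined protocol and SAP*

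**What the plan says.** The regimen is fixed in two places. Section 6.3.1: "Ipilimumab will be administered in accord with the official prescribing information: 3 mg/kg intravenously once every 3 weeks, for 4 doses". The Synopsis, under Treatment Regimen: "Ipilimumab will be administered at 3 mg/kg IV infusion on days 1, 22, 43, and 64".

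Section 6.5.2 covers visits delayed for reasons other than toxicity. Its Table 7 states for each visit what is given and "whether a protocol violation should be reported and recorded". The section adds: "The range of days is counted from the original scheduled date". The rows that matter here are:

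| Visit | Window | Ipilimumab listed | Deviation |
|---|---|---|---|
| Day 22 (dose 2) and day 43 (dose 3) | ±2 days | yes | No |
| Day 22 and day 43 | ±3 to 7 days | yes | Yes |
| Day 64 (dose 4) | ±7 days | yes | No |
| Day 64 | ±8 to 14 days | yes | Yes |
| Day 64 | ±15 or more days | no, labs only | Yes |

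On spacing, section 6.5.2 says that a missed treatment is made up promptly, "so that subsequent treatments will be given in the appropriate intervals", and: "Treatment may be continued for an additional time period, if needed". It also says: "Participants who are treated outside of the established schedule should return to the original schedule as soon as possible". None of this gives a number of days, and no other section sets a minimum gap between ipilimumab doses.

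**The concern.** The windows are anchored to the calendar, not to the previous dose, and the window at day 64 is much wider than at the earlier doses. If its minus side is used, the gap between doses 3 and 4 can fall far below 3 weeks while the table records no deviation. The regimen and the compliance table then give different answers for the same visit.

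Safety is a primary objective, and section 8.2.1 notes that ipilimumab toxicities can be severe, though managed well with steroids. The study calendar has imaging only (day 57) between days 43 and 64, with no adverse event assessment, physical examination or laboratory tests. An early day 64 visit therefore shortens the time in which toxicity from dose 3 can show itself before dose 4 is given.

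**Working it through.** **Inputs.** Planned days 1, 22, 43 and 64 (Synopsis). Interval of 3 weeks (section 6.3.1). Windows and their anchor (section 6.5.2, Table 7). Day 1 is taken as the day of dose 1, and the later windows are used as printed, including the minus side.

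**The plan's own figure.** 22 - 1 = 43 - 22 = 64 - 43 = 21 days. The planned days agree with every 3 weeks.

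**No-deviation days.** Dose 2: 22 ± 2 = days 20 to 24. Dose 3: 43 ± 2 = days 41 to 45. Dose 4: 64 ± 7 = days 57 to 71.

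**No-deviation gaps.** Shortest = earliest later dose minus latest preceding dose. Longest = latest later dose minus earliest preceding dose.

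| Gap | Shortest | Longest |
|---|---|---|
| Dose 1 to 2 | 20 - 1 = 19 | 24 - 1 = 23 |
| Dose 2 to 3 | 41 - 24 = 17 | 45 - 20 = 25 |
| Dose 3 to 4 | 57 - 45 = **12** | 71 - 41 = 30 |

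If the ±2 printed at day 1 is applied as well, the shortest gap from dose 1 to 2 is 20 - 3 = 17 days. After an on-time dose 3, the shortest gap to dose 4 is 57 - 43 = 14 days.

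**Where the short gaps come from.** Split by the day of dose 4:
- Days 57 to 61 (3 to 7 days early): 57 - 45 = 12 to 61 - 41 = 20 days.
- Days 62 to 63: 62 - 45 = 17 to 63 - 41 = 22 days.
- Days 64 to 71: 64 - 45 = 19 to 71 - 41 = 30 days.

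There are 5 × 15 = 75 in-window pairs of days. Of these, 5 + 4 + 3 + 2 + 1 = 15 are under 17 days apart, and all 15 have dose 4 on days 57 to 61. This counts pairs of days; it is not a frequency.

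**Flagged rows.** The early side of ±8 to 14 days is days 50 to 56, which is 50 - 43 = 7 to 56 - 43 = 13 days after an on-time dose 3. Separately, returning to the original schedule after a dose given 7 days late leaves 43 - 29 = 14 or 64 - 50 = 14 days. After dose 2 on day 29, every no-deviation date for dose 3 is 41 - 29 = 12 to 45 - 29 = 16 days later, while keeping 21 days (day 50) is logged as a deviation.

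**Check of the remedy.** With -2/+7 days at day 64, the in-window gap is 62 - 45 = 17 to 71 - 41 = 30 days. The window alone is not enough: dose 3 on day 50 and dose 4 on day 62 would be 12 days apart. A 17-day minimum bars no date when both doses are in their no-deviation windows. After dose 2 on day 29 it puts dose 3 on day 29 + 17 = 46. Then 46 + 17 = 63, so dose 4 stays on day 64. After dose 3 on day 50 it allows dose 4 from day 67.

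**The case against.** **The table is about lateness.** Its title and section concern delays, its footnote attaches ± to the word for delay, and even the day 1 row carries ±. The minus sign may be template notation. Taken wholly literally, the flagged rows would let doses 3 and 4 both fall on day 50 (43 + 7 and 64 - 14), which nobody intends. So a reader might infer that the authors meant to allow early dosing, and the documents do not support that. But the minus side is printed, no text limits it to late visits, and staff who schedule from the table have no other number.

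**The regimen governs.** Section 6.3.1 ties dosing to the prescribing information, and Table 7 does not claim to override it. Section 9.1.5 defines a violation broadly enough that a 12-day gap may be reportable anyway. A reader might infer that such a gap would escape reporting; that goes too far. What stands is that the two sections can give opposite answers.

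**No consequence is shown.** This stands. The documents link higher ipilimumab toxicity to dose (10 against 3 mg/kg), not to spacing. Clinical and laboratory checks accompany dose 4, stopping bounds apply, and the monitoring committee meets monthly.

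**Some routes are already flagged.** This also stands. The 7-day and return-to-schedule figures are not compliant gaps. They show only why a minimum interval is needed alongside the new window.

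**Seventeen days has no clinical source.** True. It is the tolerance that the ±2 windows already imply for doses 2 to 3, which is why the rule defers to any longer minimum in the prescribing information.

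**The vaccine footnote.** Table 7 says: "A participant will be taken off protocol treatment if more than one vaccination is delayed", with ±3 to 7 days in brackets. A reader might infer that holding ipilimumab would end protocol treatment, so that this footnote must change too. It need not. Under a 17-day minimum the day 29 case makes at most one paired vaccine late (day 46), and section 6.5 lets either agent be delayed alone. Under a longer minimum of 19 days or more, paired visits could make two vaccines late, but giving the vaccine on time avoids that.

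**Conclusion.** The inconsistency is real. As printed, Table 7 allows a no-deviation gap of 12 days between doses 3 and 4 (14 after an on-time dose 3) against a stated 21. Only dose 4 given 3 to 7 days early produces a no-deviation gap under 17 days. The result rests on applying the printed minus side at day 64 and on no minimum interval being stated elsewhere.

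A reader might go on to infer excess toxicity or a distorted count of dose-limiting toxicities. The documents support neither: they give no data on shortened intervals and no basis for how often one would occur. Sample size and power are untouched. This is a minor safety correction, worth making because it is specific and cheap.

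**What to change.** 1. In the day 64 rows of Table 7, give ipilimumab its own entries, leaving the vaccine 5 and laboratory windows as they are:
   - -2 to +7 days (days 62 to 71): given, no deviation.
   - +8 to +14 days (days 72 to 78): given, deviation.
   - +15 days or more: not given, as now.
   - Never given more than 2 days early.
2. Add to section 6.5.2: *Ipilimumab is given no sooner than 17 days after the preceding dose, or after a longer minimum if the prescribing information requires it. This prevails over the Table 7 windows and over return to the original schedule. A shorter interval is a deviation. If ipilimumab is held for this reason, the vaccine may be given on time.*

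The vaccine discontinuation footnote stays as it is.

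Cost: edits to one block of the table and a short rule. In practice this means an occasional later dose, an extra logged deviation (for example dose 3 on day 46 after dose 2 on day 29), or a separate ipilimumab visit when vaccine 5 is given before day 62.

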# 6.6 Discontinuation of Therapy

Protocol treatment includes both the 6MHP vaccine and ipilimumab. Either or both may be discontinued for any of the following reasons:

Protocol treatment will be discontinued for a participant for any of the following reasons:

 Any dose-limiting toxicity (DLT), as defined in Section 9 warrants discontinuation of the agent to which the DLT is attributed. If a DLT attributed to one intervention is not believed to be related to the other treatment, only the one to which the DLT is attributed must be discontinued. However, management of toxicities attributed to ipilimumab should follow current standard practice guidelines, including use of steroids when indicated.

- Disease progression requiring other therapy (e.g. surgery under general anesthesia, radiation, chemotherapy, or steroid therapy). The appearance of small metastases or recurrent tumor deposits will not be a basis for discontinuing the vaccinations. Biopsy to determine the nature of new lesions, or minor surgical procedures to excise a new lesion, will not be a basis for discontinuing vaccinations. Also, surgery to perform biopsy of tumor at day 22, in accord with the protocol, will not be a basis for discontinuing therapy, whether done under local anesthesia or general anesthesia.
- Initiation of cytotoxic chemotherapy, radiation therapy, or targeted therapy for melanoma or other cancer.
- Initiation of non-permitted medication, or other systemic immunosuppressive therapy, except that steroid or immunosuppressive therapy for management of toxicities of ipilimumab is allowed without discontinuation of vaccines.
- Any other potential adverse reaction deemed sufficiently serious to warrant discontinuation of therapy by the Principal Investigator or one of the Associate Investigators.
- Noncompliance with the requirements of the study.
- Therapy may be discontinued at the participant's request.
- Therapy may be discontinued at the discretion of an Investigator.
- Pregnancy. Pregnant participants will continue to be followed for the duration of the pregnancy.
- Treatment delays as specified in section 6.5.1.

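### Table 7's removal footnote counts 3 to 7 day delays for all six vaccines, but at vaccines 5 and 6 those delays are inside the no-deviation window

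*Combined protocol and SAP*

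**What the plan says.** Section 6.5.2 deals with visits delayed for reasons other than toxicity. It introduces Table 7 as the table that "defines what constitutes a delayed visit, whether the participant should continue to be treated, and whether a protocol violation should be reported and recorded", and states: "The range of days is counted from the original scheduled date".

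Each row of Table 7 gives three ranges of days, what is done at the visit, and whether a deviation is recorded. The headings for vaccines 1, 2-3, 4, 5 and 6 all carry an asterisk. The asterisked footnote reads "A participant will be taken off protocol treatment if more than one vaccination is delayed", followed by a bracketed range of 3 to 7 days either side, and it applies throughout the treatment period.

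Section 6.6 says "Protocol treatment includes both the 6MHP vaccine and ipilimumab". Its list of reasons for stopping refers to delays only as "Treatment delays as specified in section 6.5.1", which is the section on toxicity delays. It does not cite 6.5.2 or Table 7.

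**The concern.** The footnote uses one range for every vaccine, but Table 7 uses two sets of windows. The 3 to 7 day range fits the rows for vaccines 1 to 4, whose no-deviation window is 2 days. It does not fit the rows for vaccines 5 and 6, whose no-deviation window is 7 days. In those two rows the same table accepts a 3 to 7 day shift, yet the footnote counts it towards mandatory removal. The longer shift that is a deviation there is not named at all.

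A rule that ends treatment should not contradict the table it annotates. Applied as written, it can cost a participant a vaccination because of a visit that met the schedule. Two coordinators could also handle identical visits differently.

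**Working it through.** No figure in the plan rests on this footnote, so the check is a comparison of the footnote with each row of Table 7.

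**Step 1. Windows by vaccine (days from the scheduled date, either side).**

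| Vaccine | Day | No deviation | Vaccine given, deviation | Vaccine not given | Where a 3 to 7 day shift falls |
|---|---|---|---|---|---|
| 1 | 1 | up to 2 | 3-7 | 8 or more | deviation band |
| 2 | 8 | up to 2 | 3-7 | 8 or more | deviation band |
| 3 | 15 | up to 2 | 3-7 | 8 or more | deviation band |
| 4 | 43 | up to 2 | 3-7 | 8 or more | deviation band |
| 5 | 64 | up to 7 | 8-14 | 15 or more | no-deviation window |
| 6 | 85 | up to 7 | 8-14 | 15 or more | no-deviation window |

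Footnote and table agree for vaccines 1 to 4 and conflict for vaccines 5 and 6.

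**Step 2. Size of the overlap on the late side.** Day 64: accepted late days are 65 to 71 (7 days), and 64 + 3 to 64 + 7 = Days 67 to 71 (5 days). Day 85: accepted late days are 86 to 92 (7 days), and 85 + 3 to 85 + 7 = Days 88 to 92 (5 days). At each of these visits, 5 of the 7 accepted late days fall in the removal band.

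**Step 3. Which pairs of delays are affected.** Removal needs more than one counted delay. Six vaccines give 6 × 5 / 2 = 15 pairs. Pairs within vaccines 1 to 4 number 4 × 3 / 2 = 6, and there the footnote works as the table suggests. The other 15 − 6 = 9 pairs include vaccine 5 or 6, so at least one counted delay is an accepted visit. In one of them (vaccines 5 and 6) neither visit is a deviation.

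**Step 4. What is lost.** The 9 pairs split by where the second delay falls:

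- Second delay at vaccine 5 (with vaccine 1, 2, 3 or 4): 4 pairs. The Day 64 row directs that vaccine 5 and ipilimumab be given for any shift up to 14 days. If staff follow that row and then stop, vaccine 6 is lost, which is 1 of 6.
- Second delay at vaccine 6 (with any of vaccines 1 to 5): 5 pairs. If vaccine 6 is given as its row directs, no protocol dose is left to lose. If it is withheld, again only vaccine 6 is lost.

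The synopsis states "Ipilimumab will be administered at 3 mg/kg IV infusion on days 1, 22, 43, and 64", so by the end of the Day 64 visit no scheduled ipilimumab dose remains.

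**Step 5. The reverse anomaly.** Vaccines 5 and 6 each given 5 days late: no deviation recorded, but both lie in the footnote's range, so removal is triggered. Vaccines 5 and 6 each given 10 days late: two deviations recorded, but neither lies in the range, so removal is not triggered.

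**Step 6. Statistical quantities.** The 18/24 rule in section 8.3 has P(X ≥ 18) = 0.036 at a 55% response rate and 0.811 at 80%, consistent with the stated 80% power. Neither uses anything from Table 7.

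**The case against.** The best defence is that an in-window visit is not delayed, because the text says Table 7 defines a delayed visit. This is a sensible reading and some staff would adopt it. It does not settle the matter: no column labels a range as delayed, the footnote states its own range, and the asterisk is on vaccines 5 and 6. A second defence is that recording a deviation and counting towards removal are separate functions, so an unreported shift could still count as cumulative drift. That is possible, but it does not explain why the larger 8 to 14 day shift is left out. What is established is therefore a conflict on the literal text, not that accepted visits will in fact cause removals.

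Two stronger readings are tempting and the documents do not support them.

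- **A single late Day 43 visit leads by itself to removal.** Section 6.3.1 sets ipilimumab at "3 mg/kg intravenously once every 3 weeks, for 4 doses". A 3 to 7 day delay at Day 43 (Days 46 to 50) plus 21 days gives Days 67 to 71, exactly the overlap. But this assumes the shift must be carried forward. Section 6.5.2 says: "Participants who are treated outside of the established schedule should return to the original schedule as soon as possible". No minimum ipilimumab interval is stated. Returning to Day 64 leaves 64 − 50 = 14 to 64 − 46 = 18 days, while Table 7 itself accepts Day 45 followed by Day 57, which is 12 days, without a deviation. A visit on Day 64, 65 or 66 avoids the band.
- **The participant also loses vaccine 5 and the fourth ipilimumab dose.** This requires removal before treatment at the Day 64 visit, against that row's instruction to give both. The rows for vaccines 1 to 4 also give vaccine in the counted band, so treating at the visit and then stopping is the reading that fits every row. Section 6.6 also allows either agent, not necessarily both, to be stopped.

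The effect on the trial is also limited. The tumour and node biopsies are on Day 22, before the overlap. Under section 8.2.2, eligible participants who received any protocol treatment remain in the immune response evaluation.

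**Conclusion.** The inconsistency is real and minor. The footnote's single range matches the deviation band for vaccines 1 to 4 and contradicts the accepted window for vaccines 5 and 6. No other section resolves it. The main case is one 3 to 7 day deviation among vaccines 1 to 4 followed by an accepted 3 to 7 day shift at Day 64, and the realistic cost is vaccine 6.

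That cost rests on two assumptions: that staff apply the footnote literally, and that they follow the Day 64 row before stopping treatment. The documents give no frequency of late visits, so the number of participants affected cannot be estimated. A reader might infer that the trial's conclusions are at risk. Nothing supports this: sample size, power and the 18/24 rule are unchanged.

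**What to change.** Keep the opening of the footnote, "A participant will be taken off protocol treatment if more than one vaccination is delayed", and replace the bracket with: *into its deviation band in Table 7 (± 3 to 7 days for vaccines 1-4; ± 8 to 14 days for vaccines 5-6)*.

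This stops accepted visits at Days 64 and 85 from counting. It also makes the 8 to 14 day deviations at those visits count, on the same principle as the earlier rows. The sponsor should confirm that this is the intent. Whether delays long enough for the vaccine to be withheld should also count is a separate sponsor choice and is not part of this change.

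Optionally, cite 6.5.2 and Table 7 next to 6.5.1 in the delay item of section 6.6.

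The cost is one reworded footnote and, if wanted, one cross-reference in a routine amendment. Visits, assays and sample size do not change.
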